1.2.1.2. Safety

1.2.1.2.1. Pooled Safety 16 Week Data From Phase 3 Studies CC-10004-PSA-002 (Palace 1), CC-10004-PSA-003 (Palace 2), CC-10004-PSA-004 (Palace 3), and CC-10004-PSA-005 (Palace 4)

The safety data from the Palace 1, 2, 3, and 4 studies were pooled and summarized for the first 16 weeks of exposure to placebo or apremilast (Celgene, 2017; Wells, 2013). The analyses conducted on the apremilast population included subjects started on apremilast at baseline and subjects switched from placebo to apremilast at Weeks 16 or 24. Analysis included all data during the time subjects were exposed to apremilast, regardless of the time apremilast exposure started.

Approximately half of the subjects (50.7%) experienced ≥1 treatment-emergent adverse event (TEAE) during the first 16 weeks of exposure to apremilast. The incidence of TEAE was higher among subjects who received apremilast than placebo (42.9%) (Table 8). The most frequently reported TEAEs were diarrhea, nausea, headache, and upper respiratory tract infection. The subject incidence of diarrhea, nausea, and headache was higher in the APR 30 BID group than in the APR 20 BID group, suggesting a dose effect.

Table 8: Treatment-Emergent Adverse Events Reported in ≥ 2% of Subjects in Any Treatment Group, First 16 Weeks of Exposure (Studies CC-10004-PSA-002, CC-10004-PSA-003, CC-10004-PSA-004, and CC-10004-PSA-005; Subjects as Treated)

	Weeks 0 to 16	First 16 Weeks of Apremilast Treatmen		
Preferred Term ^a	Placebo Subjects n (%) (N = 671)	APR 20 BID n (%) (N = 972)	APR 30 BID n (%) (N = 973)	APR Total n (%) (N = 1945)
Any TEAE	288 (42.9)	470 (48.4)	516 (53.0)	986 (50.7)
Diarrhea	17 (2.5)	86 (8.8)	128 (13.2)	214 (11.0)
Nausea	26 (3.9)	71 (7.3)	114 (11.7)	185 (9.5)
Headache	24 (3.6)	53 (5.5)	77 (7.9)	130 (6.7)
Upper Respiratory Tract Infection	16 (2.4)	42 (4.3)	37 (3.8)	79 (4.1)
Vomiting	5 (0.7)	17 (1.7)	29 (3.0)	46 (2.4)
Nasopharyngitis	12 (1.8)	28 (2.9)	17 (1.7)	45 (2.3)
Hypertension	15 (2.2)	17 (1.7)	25 (2.6)	42 (2.2)
Dyspepsia	8 (1.2)	21 (2.2)	19 (2.0)	40 (2.1)
Abdominal Pain Upper	1 (0.1)	19 (2.0)	18 (1.8)	37 (1.9)

AE = adverse event; APR = apremilast; BID = twice daily; MedDRA = Medical Dictionary for Regulatory Activities; TEAE = treatment-emergent adverse event.

Treatment-emergent AEs were predominantly mild or moderate in severity. The most frequently reported TEAEs (ie, diarrhea, nausea, upper respiratory tract infection, and headache) were primarily mild in severity. Severe diarrhea was reported by 1 (0.1%) subject in the placebo group, 4 (0.4%) in the APR 20 BID group, and 3 (0.3%) in the APR 30 BID group. Severe nausea was reported by 0 subjects in the placebo group, 2 (0.2%) in the APR 20 BID group, and 3 (0.3%) in the APR 30 BID group. Severe headache was reported by 1 (0.1%) subject in the placebo group, 2 (0.2%) in the APR 20 BID group, and 1 (0.1%) in the APR 30 BID group. No events of severe upper respiratory tract infection were reported in any treatment group. Treatment with apremilast was associated with an increase in adverse reactions of depression. During the 0-to-16-week placebo-controlled period of Palace 1, 2, and 3, 1.0% (10/998) of patients treated with apremilast reported depression or depressed mood and 0.8% (4/495) treated with placebo.

^a Preferred terms are coded using MedDRA Version 14 and are presented in descending order of subject incidence in the APR Total group. A subject with multiple occurrences of an AE is counted only once in the AE category.

^b The first 16 weeks of exposure are included regardless of when apremilast exposure started.

Body weight was measured routinely in Studies CC-10004-PSA-002, CC-10004-PSA-003, CC-10004-PSA-004, and CC-10004-PSA-005. At the end of the placebo-controlled period, median (mean) weight change from baseline was 0.00 (0.13) kg in the placebo group, -0.50 (-1.05) kg in the APR 20 BID group, and -0.60 (-0.97) kg in the APR 30 BID group. Weight loss > 5% was observed in 2.1% of subjects in the placebo group, 4.7% in the APR 20 BID group, and 4.9% in the APR 30 BID group.

Serious TEAEs were reported for 22 (3.3%) subjects who received placebo and 44 (2.3%) who received apremilast during the first 16 weeks of exposure (Table 9). The incidence of serious adverse events (SAEs) was comparable across treatment groups, ie, 3.3% of subjects in the placebo group, 2.4% in APR 20 BID group, and 2.2% in the APR 30 BID group.

Table 9: Treatment-Emergent Serious Adverse Events Reported in > 1 Subject in Any Treatment Group, First 16 Weeks of Exposure (Studies CC-10004-PSA-002, CC-10004-PSA-003, CC-10004-PSA-004, and CC-10004-PSA-005; Subjects as Treated)

	Weeks 0 to 16	First 16 Weeks of Apremilast Treatmen		

The long-term safety of apremilast monotherapy in patients who had received ≤ 1 csDMARD was assessed in the ACTIVE study over a period of 52 weeks (Nash, 2018). The overall incidence of AEs in the placebo-controlled period was generally similar for APR monotherapy and placebo. The most commonly reported AEs ($\geq 5\%$ of patients) with APR vs placebo were nasopharyngitis (8.3% vs 6.4%, respectively), nausea (8.3% vs 1.8%), headache (7.3% vs 3.7%), hypertension (6.4% vs 6.4%), and diarrhea (patient- or investigator-reported) (14.7% vs 11.0%); using a protocol-defined characterization of diarrhea (≥ 2 watery/liquid stools/day), overall incidence was lower for APR and placebo (11.0% and 8.3%). Serious AEs were lower with APR than placebo (2.8% vs 4.6%). No opportunistic infections, reactivations of tuberculosis (TB), or cases of marked depression were seen. In general, no increase was seen in AE incidence/severity with longer-term exposure to APR up to 52 weeks. Apremilast was generally well tolerated.

The long-term safety of apremilast, with or without concomitant csDMARDs, over 4 years was assessed in a pooled analysis of the Palace 1, 2, and 3 studies (Mease, 2017). Results from this analysis suggested a favorable and consistent safety profile over time. Importantly, the frequency of gastrointestinal AEs decreased with longer exposure to apremilast, and the frequency of other common AEs either decreased or remained stable with prolonged exposure (Table 10). The rates of infections did not increase over time, nor did the data indicate a need for specific laboratory monitoring.

Treatment with apremilast was associated with an increase in adverse reactions of depression; 0.3% (4/1441) of patients treated with apremilast discontinued treatment due to depression or depressed mood vs 0 placebo-treated patients (0/495). Depression was reported as serious in 0.2% (3/1441) of patients exposed to apremilast vs 0 placebo-treated patients (0/495). Two patients who received placebo committed suicide vs 0 apremilast-treated patients. Importantly, the rates of depression remained low over time.

Table 10: Frequency of Common AEs Over 208 Weeks of Exposure

APR-Exposure Period*	Weeks 0 to ≤ 52	Weeks > 52 to ≤ 104	Weeks > 104 to ≤ 156	Weeks > 156 to ≤ 208
Subjects, n (%)	APR30 N=721	APR30 n=520	APR30 n=443	APR30 n=401
≥ 1 AE	524 (72.7)	316 (60.8)	284 (64.1)	234 (58.4)
≥1 SAE	47(6.5)	35 (6.7)	40 (9.0)	28 (7.0)

nasopharyngitis, and urinary tract infection; most AEs were mild or moderate in severity. Apremilast 30 mg BID continued to demonstrate a favorable safety profile and was generally well tolerated.

Please refer to the IB for detailed information concerning the available pharmacology, toxicology, drug metabolism, clinical studies, and adverse event profile of the investigational product (IP).

1.3. Rationale

1.3.1. Study Rationale and Purpose

1.3.1.1. Unmet Medical Need

Apremilast has been shown to be safe and efficacious in reducing signs and symptoms of PsA, as well as improving physical function (Cutolo, 2016; Edwards, 2016; Kavanaugh, 2014; Nash, 2018). Like most agents, the clinical development program of apremilast was restricted to subjects with ≥3 swollen and tender joints at baseline. This allowed for a limited proportion of subjects with asymmetric oligoarthritis at study entry. Consequently, the safety and efficacy of apremilast in patients with oligoarthritis remains to be further investigated.

The current study is designed to evaluate the benefit: risk profile of apremilast in subjects with **an early diagnosis** of PsA (\leq 5 years since **signs and symptoms began**), presenting with oligoarthritis despite concurrent stable treatments with either NSAIDs and/or \leq 1 csDMARD.

1.3.1.2. Rationale for the Study Design

Analyses in PsA subjects with oligoarthritis (defined by different combinations of limited numbers of swollen and tender joints) in five Phase 3 PsA studies (PSA-002, PSA-003, PSA-004, PSA-005 and PSA-006) indicated that in patients with oligoarticular PsA, apremilast 30 mg BID was associated with a numerically greater proportion of subjects achieving the modified MDA (MDA-joint) at week 16 compared with placebo. In addition, results from the apremilast development program demonstrated that responses to apremilast improve over a period of up to 24 weeks when compared to placebo. Therefore, the 24-week, double-blind, placebo-controlled treatment period with frequent visits and assessments will provide adequate time to reasonably assess the onset of action of, and durability of, response to apremilast in achieving the modified MDA (MDA-Joints). The joints monitored for early escape must correspond to those affected at the Baseline Visit (sentinel joints).

The Active-treatment Extension Phase (24 weeks) will allow for the investigation of the long-term efficacy, safety and tolerability of apremilast \pm concomitant therapies for the treatment of patients with oligoarthritis. In addition, this period will allow for the investigation of the impact of apremilast \pm concomitant therapies after a course of placebo \pm NSAIDs and/or < 1 csDMARDs.

1.3.1.3. Rationale for Dose, Schedule, and Regimen Selection

The dosing regimen and dose of apremilast is based on the approved dosing regimen and dose of apremilast for the treatment of PsA.

After a dose titration over a 5-day period, an oral dose of apremilast 30 mg BID will be given to all subjects randomized or enrolled to receive apremilast.

1.3.1.4. Rationale for Choice of Comparator Compounds

The comparator of this study is Placebo. This will allow for the assessment of the risk / benefit of apremilast.

To allow for the treatment of oligoarticular PsA, apremilast \pm NSAIDs and/or \leq 1csDMARDs will be compared to placebo \pm NSAIDs and/or \leq 1 csDMARDs. Stable low doses of glucocorticoids (prednisone \leq 10 mg/day or equivalent) will be allowed. Indeed, it is understood that several patients with oligoarthritis are managed with NSAIDs and/or csDMARDs.

2. STUDY OBJECTIVES AND ENDPOINTS

Table 11: Study Objectives

Primary Objective

• The primary objective of the study is to evaluate the efficacy of apremilast 30 mg BID ± NSAIDs and/or csDMARDs vs. Placebo ± NSAIDs and/or csDMARDs in subjects with early oligoarticular psoriatic arthritis (PsA), assessed by modified MDA (MDA-Joints).

Secondary Objective(s)

- To evaluate the impact of treatment with apremilast 30 mg BID ± NSAIDs and/or csDMARDs vs. Placebo ± NSAIDs and/or csDMARDs on disease activity in subjects with early oligoarticular PsA.
- To evaluate the impact of apremilast 30 mg BID ± NSAIDs and/or csDMARDs vs. Placebo ± NSAIDs and/or csDMARDs on patient-reported outcomes (PROs) in subjects with early oligoarticular PsA.
- To evaluate the safety and tolerability of apremilast 30 mg BID ± NSAIDs and/or csDMARDs vs. Placebo ± NSAIDs and/or csDMARDs in subjects with early oligoarticular PsA.

Exploratory Objective(s)

The exploratory objectives are:

DMADDs. Computing I would stir live as a stiff in a satisfactor tire durant DADSA. Climica

csDMARDs = Conventional synthetic disease-modifying antirheumatic drugs; cDAPSA = Clinical disease activity in psoriatic arthritis (without measuring C-reactive protein);

NSAIDs = Nonsteroidal anti-inflammatory drugs; MDA = Minimal disease activity; HAQ-DI = Health Assessment Questionnaire Disability Index; PGA = Physician's Global Assessment of Disease activity; PRO = Patient-reported outcome; PsAID = Psoriatic Arthritis Impact of Disease (questionnaire).

Table 12: Study Endpoints

Endpoint	Name	Description	Timeframe
	Efficacy Endpoin	nts at Week 16: Double-Blind Placebo-Controlled Treatment Phase	
Primary	MDA-Joints	Proportion of subjects who achieve a clinical state of minimal disease activity defined MDA-Joints. Subjects must achieve ≤ 1 SJC and TJC, plus 3 out of 5 of the remaining cut-off values (BSA $\leq 3\%$; Patient pain (VAS) ≤ 15 ; Patient global disease activity (VAS) ≤ 20 ; HAQ ≤ 0.5 ; Tender entheseal points ≤ 1 (based on Leeds Enthesitis Index - LEI).	Week 16
Secondary	cDAPSA remission or low disease activity	Proportion of subjects who achieve remission (defined by clinical disease activity in psoriatic arthritis [DAPSA] \leq 4 score) or low disease activity (defined by cDAPSA > 4 but \leq 13 score).	Week 16
	Swollen Joint Count (SJC) ≤ 1	Proportion of subjects with SJC ≤ 1 .	Week 16
	Tender Joint Count (TJC) ≤ 1	Proportion of subjects with TJC ≤ 1 .	Week 16
	Patient's global assessment of disease activity	Proportion of subjects whose global assessment of disease activity score ≤ 20 in the visual analogue scale (VAS).	Week 16
	Patient's assessment of pain	Proportion of subjects whose assessment of pain score ≤ 15 in VAS.	Week 16
	PsAID-12	Change from Baseline in the Psoriatic Arthritis Impact of Disease 12-item for clinical trials (PsAID-12) questionnaire.	Week 16
	PASDAS good and moderate response	Proportion of patients achieving a good or moderate response in PASDAS score.	Week 16

Table 12: Study Endpoints (Continued)

Endpoint	Name	Description	Timeframe
	F (Double	Exploratory Efficacy Endpoints: Evaluated for the Duration of the Study: -Blind Placebo-Controlled Treatment Phase and/or the Active-treatment Phase)	
Exploratory			

Table 12: Study Endpoints (Continued)

Endpoint	Name	Description	Timeframe
	Exp	oloratory Efficacy Endpoints: Evaluated for the Duration of the Study: lind Placebo-Controlled Treatment Phase and/or the Active-treatment Phase)	
Exploratory	(Double-B	mid Flacebo-Controlled Treatment Fliase and/of the Active-treatment Fliase)	
(Continued)			

Table 12: Study Endpoints (Continued)

Endpoint	Name	Description	Timeframe
	Exp	loratory Efficacy Endpoints: Evaluated for the Duration of the ind Placebo-Controlled Treatment Phase and/or the Active-treatment	Study:
Exploratory	(Double-Di	init I facebo-Controlled Treatment I have and/of the Active-trea	atment I nase)
(Continued)			

Table 12: Study Endpoints (Continued)

Endpoint	Name	Description	Timeframe							
Exploratory (Continued)										
Safety	Safety Endpoints: Evaluated throughout the duration of the study:									
Endpoints	Adverse events	Type, frequency, severity, and relationship of adverse events (AEs) to investigational product (IP).	Throughout the duration of the study							
	Discontinuation due to AEs	Number of subjects who discontinue IP due to any AE.	Throughout the duration of the study							
	Clinically significant changes in physical examination, vital signs, and/or laboratory findings	Frequency of clinically significant changes in physical examination, vital signs, and/or laboratory findings.	Throughout the duration of the study							

3. OVERALL STUDY DESIGN

3.1. Study Design

The study will be conducted in compliance with the International Council for Harmonisation (ICH) of Technical Requirements for Registration of Pharmaceuticals for Human Use/Good Clinical Practice (GCP) and applicable regulatory requirements.

This is a Phase 4, multicenter, randomized, double-blind, placebo-controlled, parallel-group study to evaluate the efficacy, safety and tolerability of apremilast (CC-10004) in subjects with early (\leq 5 years since **signs and symptoms began**) oligoarticular PsA (according to Classification Criteria for Psoriatic Arthritis [CASPAR] criteria) despite treatment with either NSAIDs and/or \leq 2 csDMARD. Subjects must also meet the following criteria: > 1 SJ but \leq 4 SJ, and > 1 TJ but \leq 4 TJ at the Screening Visit and confirmed prior to randomization at the Baseline Visit.

Given that this is a phase 4 study, all subjects are required to meet the existing apremilast regulatory labeling conditions specific to the countries where enrollment will take place (eg, Food and Drug Administration [FDA], European Medicines Agency [EMA], Health Canada]. There is no planned protocol extension following the end of the study.

Approximately **285** subjects will be randomized in a 2:1 ratio to either apremilast 30 mg BID or identically appearing placebo, with approximately subjects assigned to the active treatment group and approximately subjects assigned to receive placebo. Treatment assignment will be stratified via an Interactive Web Response System (IWRS) based on concomitant use of glucocorticosteroids at baseline (yes/no) and prior/concomitant use of a csDMARD, either MTX or SSZ (ie, csDMARD-naïve; csDMARD use prior to baseline [treatment not continued]; or csDMARD use prior to and concomitant at baseline). The number of subjects who are csDMARD-naïve is targeted to comprise up to 50 % of the subjects enrolled in the study.

This is a 56-week study. Subjects will have up to 4 weeks in the Screening Phase, followed by 24 weeks in the Double-blind, Placebo-controlled Treatment Phase, which provides an opportunity for "early escape" at Week 16, allowing subjects to receive treatment with apremilast 30 mg BID beginning at Week 16. At the Week 24 Visit, all subjects will be offered entry into the Active-treatment Extension Phase. Subjects enrolled in the Extension Phase will receive treatment with apremilast (30 mg BID) until the end of the study (ie, up to the Week 48 Visit) or until early discontinuation.

Beginning at the Week 28 Visit, all subjects in the Extension Phase will be dispensed open-label apremilast (30 mg BID) in high-density polyethylene (HDPE) bottles (Section 7.3). Subjects, Investigators and persons responsible for the ongoing conduct of the study will continue to be blinded to the original treatment assignment. Subjects must be clearly instructed to follow dosing instructions. Subjects may discontinue at any time during the study.

After all subjects complete the Week 24 Visit (or discontinue prematurely from the study), selected members of the Amgen study team who do not have direct interaction with subjects will be unblinded for the analysis of the Week 24 data. These persons may include but are not limited

[figure not shown]
to the following: Therapeutic Area Head, Study Lead, Medical Director and the Statistician. The results from these analyses may be published prior to the end of the study.

Subjects, Investigators and persons responsible for the ongoing conduct of the study will continue to be blinded to the original treatment assignment until the end of the study. These persons are those individuals that have direct interaction with subjects and/or subject assessments, and may include but are not limited to the following: Clinical Trial Manager, Data Manager, Clinical Research Associates (Amgen and External Partners) and Site Monitors.

This is a 56-week study which will consist of 4 phases:

- Screening Phase up to 4 weeks
- Randomized, Double-blind, Placebo-controlled Treatment Phase Weeks 0 to 24. Henceforth, this will be referred to as the Placebo-controlled Phase.
 - Subjects will be randomly assigned in a 2:1 ratio to either apremilast 30 mg BID or placebo. Subjects randomized to apremilast will be dose-titrated in a blinded fashion.
 - o Dose titration is described in Study Treatments, Section 7.2. and Section 7.3.
 - Subjects with no improvement in SJC (sentinel joints) at Week 16 are eligible for early escape, at the discretion of the Investigator and will receive apremilast 30 mg BID. The joints monitored for early escape must be the "sentinel joints" (ie, the joints affected at baseline).
 - O Placebo-treated subjects who escape early will be transitioned to apremilast 30 mg BID in a blinded fashion via an Interactive Web Response System (IWRS), while apremilast-treated subjects will remain on the original treatment assigned at baseline. Placebo-treated subjects will be dose-titrated in a blinded fashion.
 - o All subjects who complete this 24-week treatment phase will have the option to enter the Active-treatment Extension Phase.
- Active-treatment Extension Phase Week 24 to Week 48. Henceforth, this will be referred to as the Extension Phase.
 - All subjects will receive apremilast 30 mg BID until the completion of the study (ie, up to the Week 48 Visit). All remaining placebo-treated subjects will be dose-titrated in a blinded fashion.
 - Beginning at the Week 28 Visit, all subjects in the Extension Phase will be dispensed open-label apremilast (30 mg BID) as described in Study Treatments and Section 7.3.
- Post-treatment Observational Follow-up Phase up to 4 weeks. Henceforth this will be referred to as the Observational Follow-up Phase.
 - All subjects who complete the Placebo-controlled Phase or the Extension Phase or discontinue early will participate in the 4-week Observational Follow-up Phase.
 - The Observational Follow-up visit should be performed 4 weeks after the last dose of IP (± 7 days).

Figure 1: Overall Study Design

^{*} Subjects with no improvement in SJC (sentinel joints) at Week 16 are eligible for early escape, at the discretion of the Investigator.

Abbreviations: BID = twice daily; csDMARD = conventional synthetic disease-modifying antirheumatic drug; MDA = Minimal Disease Activity; NSAIDs = non-steroidal anti-inflammatory drug.

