Week (Visit Window)	-28 Days	Week 0	4 (±3 days)	12 (± 3 days)	16 ^a (±3 days)	24 ^b (±3 days)	28° (±3 days)	40 (± 1 week)	48 (±1 week))	ET ^d	Obs. Follow-up Visit ^c 4 wks after the last dose of IP (± 7 days)
Patient's Assessment of Pain (VAS)	-	X	X	X	X	X	X	X	X	X	-
Dactylitis j	X										
Enthesitis assessment- LEI	-	X	X	X	X	X	X	X	X	X	-
HAQ-DI	-	X	X	X	X	X	X	X	X	X	-
BSA	-	X	X	X	X	X	X	X	X	X	-
PROs/QOLs											
PsAID-12					X						

Table 13: Table of Events (Continued)

	Screening		Placebo-controlled Phase				E	xtension Pha	Early Termination Visit	Observational Follow-up- Phase	
Visit Number	1 Screening	2 Baseline	3	4	5	6	7	8	9	Early Termination	10
Week (Visit Window)	-28 Days	Week 0	4 (±3 days)	12 (± 3 days)	16 ^a (±3 days)	24 ^b (±3 days)	28° (±3 days)	40 (± 1 week)	48 (±1 week))	ET ^d	Obs. Follow-up Visite 4 wks after the last dose of IP (± 7 days)
Health Economics Assessment											
Durtus											
Dosing Dispense Study Drug	1	X	Х	X	X	X	Х	X			
Return/Count Study Drug	-	-	X	X	X	X	X	X	X	X	-
BID = twice daily; BSA = Body Questionnaire – Disability Index Follow-up Visit = Observational	; IP = Investig	ational Pro		ported Outc	omes; PsAII	LEI = Leed	ls Enthesitis	Index;	otential; HAQ	D-DI = Health As	sessment Obs.

QOL = Quality of Life;

VAS = Visual

Analog Scale;

- ^a At the Week 16 Visit, subjects with no improvement in SJC (sentinel joints) at Week 16 are eligible for early escape, at the discretion of the Investigator and will receive treatment with apremilast 30 mg BID. The joints monitored for early escape must correspond to those affected at the Baseline Visit (sentinel joints).
- b All subjects who complete the Week 24 Visit will enter Extension Phase and receive apremilast 30 mg BID. The original treatment assignments (apremilast 30 mg BID or placebo) will remain blinded until the end of the study.
- ^c Beginning at the Week 28 Visit, all subjects in the Extension Phase will be dispensed open-label apremilast (30 mg BID) in high-density polyethylene (HDPE) bottles. Subjects must be clearly instructed to follow dosing instructions.
- ^d Subjects who discontinue the study prior to the Week 48 Visit, will have an Early Termination (ET).
- ^e The Observational Follow-up Visit will be conducted 4 weeks after the last dose of IP (± 7 days).
- f If an on site study visit is replaced with a telemedicine assessment, vital signs will not be measured.

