6.3. Observational Follow-up

6.3.1. Safety Follow-up

All subjects will be followed for 28 days after the last dose of apremilast for AE reporting, as well as SAEs made known to the Investigator at any time following the protocol-required reporting period or after end of study, as described in Section 10.

The following evaluations will be performed at the Observational Follow-up Visit, or if necessary via telephone contact, as specified in Table 13, Table of Events:

- Concomitant medications evaluation
- Concomitant procedures evaluation

• Adverse event (non-serious and serious) evaluation

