6.5.8. Adverse Events

All subjects will be monitored for adverse events (AEs) during the study. Assessments may include monitoring of any or all of the following parameters: the subject's clinical symptoms, laboratory, pathological, radiological, or surgical findings; physical examination findings; or other appropriate tests and procedures.

All AEs will be recorded by the Investigator from the time the subject signs informed consent to 28 days after the last dose of IP. Adverse events and serious adverse events (SAEs) will be recorded on the AE page of the electronic case report form (eCRF), the paper SAE reporting form (SAEs) and in the subject's source documents. All SAEs must be reported to Amgen Global Patient Safety immediately (ie, within 24 hours of the Investigator's knowledge of the event) by recording on the CRF and completing the paper SAE Report Form which is sent directly to Amgen Global Patient Safety by facsimile or email.

[figure not shown]
Details of AE reporting can be found in Section 10 of the protocol. It should be noted that worsening of a subject's psoriatic arthritis should be considered as worsening of disease under study and should not be captured as an adverse event.

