All AEs will be recorded by the Investigator from the time the subject signs informed consent until 28 days after the last dose of IP as well as any SAEs made known to the Investigator at any time following the protocol-required reporting period or after end of study will also be reported for these subjects. All adverse events (serious/non-serious) will be recorded on the CRF, the paper SAE Report form (SAEs) and in the subject's source documents. All SAEs must be reported to Amgen Global Patient Safety within 24 hours of the Investigator's knowledge of the event by recording on the CRF and completing the paper SAE Report Form which is sent to Amgen Global Patient Safety by facsimile/email.

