10.4.1. Collection of Pregnancy and Infant Health Information

Pregnancies and suspected pregnancies (including elevated β -subunit of human chorionic gonadotropin [β -hCG] or positive pregnancy test in a female subject of childbearing potential regardless of disease state) occurring while the subject is on IP, or within 28 days of the subject's last dose of IP, must be reportable within 24 hours. Investigational product is to be discontinued immediately and the subject instructed to return any unused portion of the IP to the investigator.

The pregnancy, suspected pregnancy, or positive pregnancy test must be reported to Amgen Global Patient Safety immediately by facsimile, email or other appropriate method, using the Pregnancy Notification Form or approved equivalent form (refer to Appendix X). The Pregnancy Notification Form must be submitted to Amgen Global Patient Safety within 24 hours of learning of a subject's pregnancy. (Note: Sites are not required to provide any information on the Pregnancy Notification Form that violates the country or regions local privacy laws).

After obtaining the female subject's signed consent for release of pregnancy and infant health information, the investigator will collect pregnancy and infant health information and complete the pregnancy questionnaire for any female subject who becomes pregnant while taking IP through 28 days of the subject's last dose of IP. This information will be forwarded to Amgen Global Patient Safety. Generally, infant follow-up will be conducted 12 months after the birth of the child (if applicable).

The female subject may be referred to an obstetrician-gynecologist or another appropriate healthcare professional for further evaluation.

The Investigator will follow the female subject until completion of the pregnancy and must notify Amgen Global Patient Safety immediately about the outcome of the pregnancy (either normal or abnormal outcome).

If the outcome of the pregnancy was abnormal (eg, spontaneous abortion), the Investigator should report the abnormal outcome as an AE. If the abnormal outcome meets any of the serious criteria, it must be reported as an SAE to Amgen Global Patient Safety using the paper Serious Adverse Event Report Form within 24 hours of the Investigator's knowledge of the event.

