# 5.2 Derivations of Safety Endpoints

Baseline definition for all safety endpoints is given in Section 5.3. Change from baseline is calculated as on-treatment value minus the baseline value. Handling of time points is described in Section 5.4.

Treatment-emergent Adverse Event

An AE is a treatment-emergent AE (TEAE) if the AE start date is

- on or after the date of the first dose of investigational product (IP) and no later than 28 days after the last dose of IP for subjects who have completed the study or have discontinued early by the time of database cut, or
- on or after the date of the first dose of IP for subjects who are ongoing at the time of database cut

Protocol Number: 20200058

Date: 07 February 2023

Page 31 of 67

If the treatment-emergent status of an AE is unclear due to a missing/incomplete start date, it will always be considered treatment-emergent, unless shown otherwise by data. Date imputation rules for partially missing AE start dates are described in Section 8.3.1

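### The last scheduled contact may fall as early as Day 21 after the last dose, but adverse events and pregnancies are to be collected to Day 28, so up to 7 off-drug days can pass without a scheduled inquiry.

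*Protocol*

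**What the plan says.** **Timing of the last contact.** Protocol 3.1 states: "The Observational Follow-up visit should be performed 4 weeks after the last dose of IP (± 7 days". Table 13, footnote e, repeats it: "The Observational Follow-up Visit will be conducted 4 weeks after the last dose of IP (± 7 days". The synopsis, Protocol 3.3 and the Table 13 column header carry the same window. SAP 3.1 gives 4 weeks with no tolerance. Protocol 6.3.1 allows a telephone contact where necessary, as a substitute for the visit. Table 13 lists nothing afterwards.

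**Length of collection.** The period is fixed and has no tolerance:
- Protocol 6.3.1: "All subjects will be followed for 28 days after the last dose of apremilast for AE reporting".
- Protocol 6.5.8: AEs are recorded "from the time the subject signs informed consent to 28 days after the last dose of IP".
- Protocol 10.1: AEs are recorded "until 28 days after the last dose of IP".
- Protocol 10.4.1: pregnancies "occurring while the subject is on IP, or within 28 days of the subject's last dose of IP, must be reportable within 24 hours".
- Protocol 10.4.2 and 10.4.3 use 28 days for partner pregnancies and lactation.

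**Analysis.** SAP 5.2 counts an AE as treatment-emergent if it starts "no later than 28 days after the last dose of IP for subjects who have completed the study" or have discontinued early. SAP 5.5 uses the same limit for the safety stop dates of subjects who discontinue early and for the Apremilast-exposure Period. SAP 9.4.5 uses it for medications started in the follow-up phase.

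**The concern.** The visit window and the collection period are both anchored on the last dose, but only the visit may move earlier. A site can follow Table 13 to the letter, see a subject on Day 21, and have no scheduled occasion to ask about Days 22 to 28.

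This is the trial's planned off-drug observation period, and safety and tolerability is a stated secondary objective. SAP 9.4.5 also wants follow-up medications summarised because treatment for psoriatic arthritis may be resumed or started then. For a subject seen early, the absence of a record in the last days cannot be told apart from the absence of an event.

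**Working it through.** This is calendar arithmetic. No power or sample-size formula applies.

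**Check of the plan's own figure.** Protocol 3.2 gives up to 56 weeks: 4 (screening) + 24 + 24 + 4 (follow-up) = 56. This agrees, with the visit at its nominal time of 4 × 7 = Day 28.

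**Allowed visit days.** 28 − 7 = Day 21 to 28 + 7 = Day 35.

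**Days without scheduled inquiry.** For a visit on Day v, uncovered days = max(0, 28 − v), and the share is that number divided by 28.

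| Visit day | Uncovered days | Share of 28 |
|---|---|---|
| 21 | 7 | 25.0% |
| 24 | 4 | 14.3% |
| 28 | 0 | 0% |
| 35 | 0 | 0% |

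**Average shortfall.** The documents do not say how visits will be spread, so the average per subject could lie anywhere from 0 days (all seen on Day 28 or later) to 7 days (all seen on Day 21). As an illustration only, assume visits are spread evenly over the 15 days from Day 21 to Day 35:
- Share seen before Day 28: 7/15 = 47%.
- Mean shortfall: (7 + 6 + 5 + 4 + 3 + 2 + 1)/15 = 28/15 = 1.9 days.
- Share of the window: 1.87/28 = 6.7%.

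**Where the shortfall enters the analysis.**
- Subject incidence divides by the number of subjects (SAP 9.6.1).
- The exposure-adjusted rate divides by treatment duration, cut at the first event (SAP 9.6.1). Treatment duration runs from first to last dose (SAP 9.6.9).
- The 28-day tail is therefore in no denominator. Missed events can only lower numerators.

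**Who is affected in the placebo-controlled comparison.** There the 28-day tail concerns subjects who discontinue early (SAP 5.5 and 9.6.1). If the 15% dropout assumed in Protocol 9.3 applies, that is 0.15 × 285 = 42.75, about 43 subjects over both arms.

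**Side check on stated durations.** A Day 35 visit makes the follow-up phase 5 weeks and the total 4 + 24 + 24 + 5 = 57 weeks. The stated maxima are 4 and 56.

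**The case against.** The strongest reply is that the duty to collect does not end with the visit. Protocol 6.3.1 states 28-day follow-up as a requirement in its own right, and nothing bars a call on Day 28. Protocol 10.1 and 10.5 keep SAEs reportable whenever they become known, and 10.4.1 keeps pregnancies to Day 28 reportable within 24 hours. The ±7 days in Table 13 was also a deliberate addition in Amendment 5. All of this stands and limits the point, but it leaves the gap open: reporting that waits for the subject to speak up is weaker than a scheduled question.

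Four stronger readings are tempting, and the documents do not support them.
- **That sites cannot comply.** They can, by making an unscheduled contact. What is missing is a scheduled one.
- **That the SAP assumes every subject is observed to Day 28.** SAP 5.2 sets an upper limit for counting events. It makes no claim of complete observation, and person-time is not inflated.
- **That late SAEs and pregnancies are lost.** They remain reportable if known. For pregnancy, Table 13 schedules no test at this visit. The last is at Week 48 or Early Termination, so a later contact restores the question but not test-based detection.
- **That a quarter of the window is typically lost, or that a trial-wide total of lost subject-days can be given.** 25% is the worst case for one subject. Any total needs a visit distribution that the documents do not supply.

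A further reply is that Protocol 3.3 treats such a subject as complete. This has little analytic weight, since the same section defines completion for analysis as reaching the Week 48 Visit.

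**Conclusion.** The mismatch is real and sits in the current text. A compliant schedule can leave up to 7 of 28 off-drug days (25% at worst, none for visits on Day 28 or later) without a scheduled inquiry. The exposure is mainly to non-serious AEs and newly started medications on Days 22 to 28, plus pregnancies that nobody reports.

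Denominators are unaffected. The effect on the randomised comparison is likely small, because both arms share the window and the tail there concerns early discontinuers. The extension has no concurrent placebo arm, so there the cost is incomplete description rather than a biased contrast.

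The 25% rests only on the stated window and collection period. The illustrative average of 1.9 days rests on an assumed even spread of visits. The change is worth making because it is cheap and closes a gap that following the schedule as written leaves open.

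**What to change.** Either of two changes closes the gap.

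1. **One-sided window.** In the synopsis, Protocol 3.1, 3.3 and Table 13 (header and footnote e), set the visit at 28 days after the last dose with a window of 0 to +7 days. Uncovered time falls to 0 of 28 days. Day 35 is already allowed, so the latest visit does not move.
2. **Keep ±7 days and add a call.** For any subject seen before Day 28, require a telephone check on or after Day 28 that asks about AEs, medications and pregnancy.

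With either change:
- State in Protocol 3.3 that a subject seen before Day 28 still counts as a completer once the Day 28 contact is made. Otherwise a Day 27 visit under a one-sided window could class the subject as an early discontinuation.
- Align the 4-week phase length and the 56-week total, which visits on Days 29 to 35 already exceed.

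The SAP's Day 28 cut-off needs no change. The cost is slightly less scheduling freedom under the first option, or one short call per subject seen early under the second. No site visit is added, since the contact may already be by telephone.

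If follow-up is already complete, report how many subjects had their last contact before Day 28.
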